## 10.0 Treatment/Follow-up Decision at Evaluation of Patient

## 10.1 Continuation of treatment

Patients who are responding and show signs of clinical improvement to treatment per the investigator's judgement will continue treatment per protocol.

## 10.2 Clinical deterioration

Patients who develop clinical deterioration while receiving therapy will go to the clinical follow-up phase.

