## 10.3 Off protocol treatment

Follow the table below for patient follow-up after patient goes off protocol treatment.

CFU=Clinical Follow-Up

Reason Off Treatment	Go to CFU, or end follow-up
Treatment (Intervention) Completed Per Protocol Criteria	CFU
Patient Withdrawal/Refusal After Beginning Protocol Therapy (Intervention)	CFU
Adverse Events/Side Effects/Complications	CFU
Clinical deterioration During Active Treatment (Intervention)	CFU
Alternative Therapy	No follow-up
Patient Off-Treatment (Intervention) For Other Complicating Disease	CFU
Death On Study	No follow-up
Other	CFU
Clinical deterioration Before Active Treatment (Intervention)	No follow-up
Patient Withdrawal/Refusal Prior To Beginning Protocol Therapy (Intervention)	No follow-up

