## 10.4 Clinical Follow-up occurs at Day 28 and Day 56 after registration unless patient withdrawal has occurred.

If the patient has achieved clinical improvement, the patient will be observed at 56 days, from time of registration.

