## 12.0 Treatment Evaluation Criteria

The ordinal scale used for assessment of the clinical and respiratory status on each day of the study is included below. Each day, the worst (i.e., highest ordinal) score from the previous day will be recorded, i.e., on Day 3, the highest ordinal score from Day 2 is obtained and recorded for Day 2. The scale is as defined by the WHO as follows:

Patient State	Descriptor	Score
Uninfected	No Clinical or Virological Evidence of Infection	0
Ambulatory	No Limitation of activities	1
	Limitation of activities	2
Hospitalized, Mild Disease	Hospitalized, no oxygen therapy	3
	Oxygen by mask or nasal prongs	4
Hospitalized, Severe Disease	Non-invasive ventilation or high flow oxygen	5
	Intubation and Mechanical Ventilation	6
	Ventilation + additional organ support-pressors, RRT, ECMO	7
Dead	Death	8

In addition, patients will be stratified at baseline based on the ordinal scale below. A score of 3-4 is associated with hospitalized with mild disease versus score of 5 is associated with severe disease.

The primary outcome assessment for efficacy will be evaluated based on the number of patients who are alive AND respiratory failure-free at Day 28 after study entry.

Respiratory failure at Day 28 will be defined by clinical diagnosis of respiratory failure corresponding to a score of 5-8 on the above ordinal scale at Day 28. Specifically, respiratory failure is defined by meeting any of the following criteria:

- Requiring ICU admission,
- mechanical ventilation,
- ECMO,
- non-invasive ventilation,
- or high flow oxygen devices,

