#### 13.5 Secondary Analyses

1. Proportion of patients alive AND free of ventilator use / ECMO at Day 28: The proportion will be evaluated based on the number of patients who are alive AND free of

ventilator use or ECMO at Day 28 after study entry divided by the number of total patients enrolled for each treatment arm. The proportion of patients who have this event will be analyzed similarly to the primary endpoint. Comparisons will be done by use of independent samples Z-test for proportions and a 95% confidence interval will be constructed for the difference between groups. The Cochran-Mantel-Haenszel test will be used to include stratification factors. Multivariable logistic regression models will be used to assess the influence of treatment arm on while adjusting for other factors of interest.

**2. Time to death and Mortality rate:** The Kaplan-Meier method will be used evaluate differences in the distributions of time-to-death between treatment arms. Rates of mortality at day 28 and day 56 mortality will be estimated. Patients lost to follow-up or who withdraw early will be considered censored at their last assessment date for the Day 28 rate. The stratified log-rank test will be used to compare differences in distributions of time to death based on stratification factors. Cox proportional hazards model will be used to compare treatment arms with inclusion of stratification factors or adjustment for covariates of interest.

**3. Time to clinical improvement:** Time to clinical improvement will be evaluated using Kaplan-Meier methods and Cox regression models. Rates of clinical improvement at days 14 and 28 will be estimated. Time to clinical improvement will be assessed after all patients have reached day 14 and 28; no clinical improvement at day 14 or 28 or death before day 14 or 28 will be considered as right censored. Hazard ratios with 95% confidence intervals will be calculated by the Cox proportional-hazards model. Covariates of interest will be included in regression models.

**4. Clinical status at Days 14 and 28:** The distribution of the clinical status will be summarized by arm at days 14 and 28. A proportional odds model with treatment arm and disease severity at baseline as covariates will be used to evaluate whether the odds of improvement on the ordinal scale are higher for the treatment arm as compared to control.

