#### Missing Data Considerations

All efforts will be made to minimize the occurrence of missing data. Subjects who discontinue treatment in either arm will be encouraged to remain in the study and to continue with follow-up visits for key outcomes at Day 28 and 56.

For time to event outcomes, subjects who are lost to follow-up or withdrawal from the study prior to Day 28 and prior to observing/experiencing the event will be censored at the time of their last observed assessment.

For duration of non-invasive ventilation/high-flow oxygen, ventilation/ECMO or supplemental oxygen, subjects will be considered to have the event of interest until Day

28 if they have the event of interest at their last follow-up assessment day before Day 28 in the case of lost to follow-up or patient withdrawal. Likewise, if they do not have the event of interest at their last follow-up assessment, they will be considered to not have this event through Day 28.

If the subject is discharged and no further hospitalization data are available, then the subject will be assumed to not have been readmitted to the hospital.

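### After deterioration or stopping study drug, Section 10 requires assessments only at Days 28 and 56 while Section 12.0 wants a daily score; Day 14 status could be lost selectively, and no rule handles the gap

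*Combined protocol and SAP*

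**What the plan says.** Several places bear on who is assessed between deterioration and Day 28.

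- **Section 10.2:** "Patients who develop clinical deterioration while receiving therapy will go to the clinical follow-up phase". No criterion for deterioration is given.
- **Section 10.3, table:** the row "Clinical deterioration During Active Treatment (Intervention)" leads to clinical follow-up. So do the rows for adverse events, refusal after starting, other complicating disease and other reasons. The row "Alternative Therapy" leads to no follow-up at all.
- **Section 10.4:** "Clinical Follow-up occurs at Day 28 and Day 56 after registration unless patient withdrawal has occurred".
- **Section 4.0:** Days 2-13 and Day 14 stand under the randomized treatment period, and Day 28 stands under follow-up. Footnote l provides telephone contact before Day 14 for discharged patients only. Footnote o lets assessments after Day 1 be done remotely.
- **Missing Data Considerations:** patients who discontinue treatment are encouraged to "continue with follow-up visits for key outcomes at Day 28 and 56".
- **Section 12.0:** "The ordinal scale used for assessment of the clinical and respiratory status on each day of the study is included below". Nothing there makes the score conditional on being on treatment.
- **Section 13.5, item 4:** "The distribution of the clinical status will be summarized by arm at days 14 and 28". The model is proportional odds, with arm and baseline severity as covariates.

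**The concern.** Section 10 and the Missing Data section agree with each other and disagree with Section 12.0. One site could stop scoring when a patient deteriorates, and another could continue. Whether a Day 14 score exists would then depend on the patient's outcome and on the site's reading of the protocol.

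Three secondary endpoints are exposed: clinical status at Day 14, improvement by Day 14, and supplemental-oxygen days in patients entering at score 4 or above. The missing values would fall on living patients who got worse, who carry much of the information on any treatment difference. The plan does not say how to handle them:

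- The exclusion rule with sensitivity analyses in Section 13.4 concerns Day 28 data.
- The carry-forward rule covers only the duration endpoints, and only after loss to follow-up or withdrawal. A patient in clinical follow-up is neither lost nor withdrawn.

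**Working it through.** **1. The plan's own figure.** The documents give no figure for Day 14, so only the denominators can be checked. For 80% vs 92%, two-sided 0.05, 80% power and unpooled variance:

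n = (0.80×0.20 + 0.92×0.08) × (1.960 + 0.842)² / 0.12² = 127.3, or 128 per arm.

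The pooled formula gives 131. Simulating the stated group-sequential boundaries at 132 per arm gives 80.3% power with binding futility. The planned 132 per arm is therefore sound and is used below.

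**2. Illustration A: planning rates borrowed for Day 14.** Assumptions, not in the documents:
- A proportion f has score 5-8 at Day 14: 20% on control and 8% on camostat.
- A share d of these are dead and scored 8.
- All survivors with score 5-7 are unscored.

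Fraction analysed = 1 − f(1−d). Observed proportion with score 4 or lower = (1−f) / [1 − f(1−d)].

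| d | Control | Camostat | Observed difference | Analysed of 132 |
|---|---|---|---|---|
| 25% | 0.80/0.85 = 0.941 | 0.92/0.94 = 0.979 | 3.8 points | 112 vs 124 |
| 50% | 0.80/0.90 = 0.889 | 0.92/0.96 = 0.958 | 6.9 points | 119 vs 127 |

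The true difference is 12.0 points. If only half of these survivors are unscored, the observed difference is 8.4 to 9.7 points. If both arms have 20% failures, the difference stays at zero, but each arm reads 89% to 94% instead of 80%.

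**3. Illustration B: loss tied to deterioration itself.** Assumptions, not in the documents:
- A proportion p deteriorates by Day 14: 25% on placebo and 12% on camostat.
- A share d = 25% of these are dead by Day 14.
- A quarter of the living deteriorators are back to score 4 or lower.
- 2% of all other patients are at score 5 or higher.
- All living deteriorators are unscored.

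True proportion with score 5-8 = p[d + (1−d)×0.75] + (1−p)×0.02:
- Placebo: 0.25×0.8125 + 0.75×0.02 = 0.218
- Camostat: 0.12×0.8125 + 0.88×0.02 = 0.115
- Difference: 10.3 points

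Observed = [pd + (1−p)×0.02] / [1 − p(1−d)]:
- Placebo: 0.0775/0.8125 = 0.095
- Camostat: 0.0476/0.91 = 0.052
- Difference: 4.3 points

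Unscored patients: 132 × (0.1875 + 0.09) ≈ 37.

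Sensitivity to d:
- At d = 10%, a true 9.8 points reads 1.8 (0.040/0.775 − 0.0296/0.892).
- At d = 40%, a true 10.8 points reads 6.5 (0.115/0.85 − 0.0656/0.928).

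A harm shrinks in the same way. With 15% deteriorating on placebo and 25% on camostat, and d = 25%, a true 7.9 points reads 3.4 (0.0775/0.8125 − 0.0545/0.8875).

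**4. The planned proportional odds model.** Two mechanisms were tried, with arm as the only covariate.
- *Uniform shift across the scale, 90% of score 5-7 survivors unscored, three assumed control distributions:* a true odds ratio of 2.0 reads 1.94 to 1.95, and 2.875 reads 2.75 to 2.77.
- *Camostat acts by preventing deterioration (rates of illustration B), all living deteriorators unscored, d from 10% to 40%, three assumed score distributions:* a full-data odds ratio of 1.44 to 1.52 reads 1.06 to 1.25. A harmful 0.73 to 0.76 reads 0.84 to 0.95.

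Both move toward 1, by very different amounts. Other distributions would give other values, so these ranges are not bounds.

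**The case against.** The strongest reply is that Section 12.0 already requires a score on each study day, and Section 14.2 collects treatment and follow-up data on the same forms. On that reading nothing is lost. This stands in part. A reader might infer from Section 10 that patients who deteriorate certainly have no Day 14 score; the documents do not support that, because collection is left unclear and is not ruled out. But the reply does not settle the matter, since two sections point the other way.

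Other stronger readings are also tempting and fail:

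- **Safety data lapse until Day 28.** Section 8.4 requires expedited SAE reporting within 30 days of the last dose. Section 8.5.2 requires grade 3 and 4 AEs on case report forms whatever the attribution, and deaths within 56 days of registration as grade 5. Only the scheduled AE evaluation is in doubt.
- **Ventilator and high-flow day counts are lost.** Section 13.3.2 counts these only in patients entering at score 6-7 and at score 5 respectively. A patient who enters at 3-4 and is later intubated belongs to neither group.
- **Day 14 compares only patients who did well.** Deaths score 8, and patients who enter severe without deteriorating may stay on schedule.
- **A stated loss of power, or a harm hidden in the trial.** Illustration B lowers the power of a Z-test on score 5-8 from about 62% to 23%. That is not the planned analysis, and every rate in it is assumed. Day 28 status and mortality remain to show a harm.

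**Conclusion.** The point holds as a conflict between Sections 10.2-10.4 with the Missing Data section on one side and Section 12.0 on the other, together with a missing rule for an absent Day 14 score. If sites follow Section 10, Day 14 data go missing because the outcome was bad, and the comparison would tend to move toward no difference.

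The documents give no rate of deterioration or discontinuation, so the size cannot be derived from them. The illustrations assume complete loss among the affected survivors, which is the unfavourable extreme. For the planned odds ratio, the result depends on how treatment acts and on the score distribution.

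Patients in clinical follow-up keep the Day 28 primary endpoint. The alternative-therapy row in Section 10.3 is an adjacent gap that can lose Day 28 as well. Should fix, for the secondary endpoints.

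**What to change.** Reconcile Sections 10.2-10.4, Section 12.0 and the Missing Data section by stating that leaving protocol treatment does not end scheduled outcome assessment. Every living patient who has not withdrawn consent to data collection keeps the ordinal score and the scheduled AE evaluation through Day 14, then at Days 28 and 56. This can be done by chart review in hospital or by telephone after discharge; footnotes l and o already allow remote contact. In the Missing Data section, replace "continue with follow-up visits for key outcomes at Day 28 and 56" with wording that covers all scheduled assessments including Day 14, and add a rule for Day 14 scores that are still missing.

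The cost is an amendment, some extra chart abstraction and some calls. Many of these patients are likely to be inpatients whose status is charted anyway. No new procedure is needed, and no treatment rule changes.

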## 10.3 Off protocol treatment

Follow the table below for patient follow-up after patient goes off protocol treatment.

CFU=Clinical Follow-Up

Reason Off Treatment	Go to CFU, or end follow-up
Treatment (Intervention) Completed Per Protocol Criteria	CFU
Patient Withdrawal/Refusal After Beginning Protocol Therapy (Intervention)	CFU
Adverse Events/Side Effects/Complications	CFU
Clinical deterioration During Active Treatment (Intervention)	CFU
Alternative Therapy	No follow-up
Patient Off-Treatment (Intervention) For Other Complicating Disease	CFU
Death On Study	No follow-up
Other	CFU
Clinical deterioration Before Active Treatment (Intervention)	No follow-up
Patient Withdrawal/Refusal Prior To Beginning Protocol Therapy (Intervention)	No follow-up

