#### 10.6 Major violation

A patient is deemed a *major violation*, if protocol requirements regarding treatment of the initial therapy are severely violated that evaluability for primary end point is questionable. If the patient received treatment, the patient may continue treatment at the discretion of the physician as long as there are no safety concerns. The patient will continue in the Active Monitoring/Treatment phase of the study, as per section 4.0 of the protocol, and all data submission should continue per protocol. If the patient does not continue with treatment, the patient will go off treatment and be followed in Clinical Follow-up.

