## 13.0 Statistical Considerations and Methodology

### 13.1 Statistical Design

The study design will be a randomized (1:1 ratio), double-blinded, placebo-controlled phase II trial of 264 patients. Randomization will be stratified based on age (< 65 years versus  $\geq$  65 years) and disease severity at study entry (hospitalized with mild disease versus hospitalized with moderate/severe disease). The purpose of this study is to evaluate the efficacy of Camostat mesilate in addition to SOC treatment as compared to SOC treatment combined with placebo with respect to clinical status on Day 28. The proportion of patients alive AND free from respiratory failure at Day 28 will be the primary outcome.

Patients will be analyzed according to their randomization assignment. All patients meeting eligibility criteria who received at least 1 dose of study drug will be included in the analysis.

Formal interim analysis will be conducted after the first 66 patients (33 treated in the treatment arm and 33 in the control group) have completed the 28 Day assessment period. Safety analyses will be done to assess occurrence of any differences in adverse events between the treatment arms. A second interim analysis will occur after 132 patients (66 in the treatment arm and 66 in the control group) have completed the 28 Day assessment period.

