### 13.3 Study Endpoints

#### 13.3.1 Primary Endpoint:

The primary endpoint will be evaluated based on the number of patients who are alive AND free from respiratory failure at Day 28 after study entry divided by the number of total patients enrolled for each treatment arm. A respiratory failure event is defined in the Treatment evaluation criteria section 12.0.

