#### 13.4 Planned Analyses

##### Primary Analysis

Frequency distributions and chi-square tests will be used to screen for major imbalances in the two randomization groups for qualitative variables; graphical displays including box plots and summary statistics (e.g., mean, median, standard deviation, ranges, etc.) will be used for quantitative variables with t-tests (after appropriate transformations if necessary to meet the assumptions of the methods).

The primary outcome will include the number of patients who are alive AND free from respiratory failure at Day 28 divided by the total number of patients in each arm. This endpoint will be analyzed in a binary fashion using properties of the binomial distribution and will be compared between randomized arms by the use of independent samples Z-test for proportions and a 95% confidence interval will be constructed for the difference between arms. Proportions will also be compared using Cochran-Mantel-Haenszel tests, including the stratification factors of age and baseline disease severity. Multivariable logistic regression models will be used to assess the influence of treatment while controlling for covariates of interest (gender, symptom onset, comorbidities) along with stratification factors. Primary analysis for this efficacy outcome will include all participants who are randomized and received at least 1 dose of study treatment. Participants will be analyzed according to the treatment to which they were randomized.

Efforts to minimize loss to-follow-up will be considerable. However, small amounts of missing data may occur. In such cases, participants without Day 28 outcome data will be excluded from the analysis. Sensitivity analyses will evaluate the impact of making different assumptions about the missing observations.

**Interim analyses:** Two interim analyses will be conducted after 25% and 50% of patients have completed the 28 day study period. The interim analysis will include the below stopping rules for efficacy and futility based on a Lan-DeMets spending function with O'Brien-Fleming boundaries. Occurrence of adverse events will also be evaluated at the interim analysis.

Accrual	Control arm (#)	Camostat arm (#)	Total number (#)	Efficacy boundary (Z scale)	Alpha spent	Futility boundary (Z scale)	Beta spent
25%	33	33	66	+/- 4.33	0.001	+/- 0.007	0.002
50%	66	66	132	+/- 2.96	0.003	+/- 0.34	0.04
100%	132	132	264	+/- 1.97	0.05	+/- 1.97	0.20

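### Section 10.3 ends follow-up for living, treated patients who leave for alternative therapy, against the Missing Data section and 10.4, and can leave survivors without the Day 28 primary outcome

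*Combined protocol and SAP*

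**What the plan says.** Section 10.3 lists ten reasons for going off protocol treatment and assigns each to clinical follow-up (CFU) or to the end of follow-up. "Alternative Therapy" is assigned to the end of follow-up.

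Four other places point the other way for patients who stop treatment:

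- Section 10.2: "Patients who develop clinical deterioration while receiving therapy will go to the clinical follow-up phase".
- Section 10.4: "Clinical Follow-up occurs at Day 28 and Day 56 after registration unless patient withdrawal has occurred". Withdrawal is the only exception it names.
- Section 10.6, on major violations: "If the patient does not continue with treatment, the patient will go off treatment and be followed in Clinical Follow-up".
- Missing Data Considerations (Section 13.5): of people who stop treatment early, whichever arm they are in, it says that they "will be encouraged to remain in the study and to continue with follow-up visits for key outcomes at Day 28 and 56".

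The primary outcome is being alive and free of respiratory failure at Day 28. The primary analysis in Section 13.4 takes everyone randomised who received at least one dose, as randomised. It then states that "participants without Day 28 outcome data will be excluded from the analysis", with sensitivity analyses that are not further specified.

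**The concern.** A site that follows the 10.3 table closes follow-up for a treated patient who moves to another therapy. A site that follows the Missing Data section asks the same patient back at Day 28 and Day 56. Both cannot be done, and no section gives a reason for treating this group differently from those who stop for toxicity, refusal or deterioration.

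What is at stake is the primary endpoint. Day 28 status is assessed in CFU, and a missing Day 28 status means exclusion. Moving to another therapy happens after randomisation and may be related to how the patient is doing. If so, excluding these patients shifts the observed rate in each arm. The shifts cancel only in special cases. Sensitivity analyses can vary assumptions about outcomes that were not collected, but they cannot recover them.

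**Working it through.** **Step 1. The table row by row (Section 10.3).**

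| Reason off treatment | Alive and treatment started? | Destination |
|---|---|---|
| Completed per protocol | Yes | CFU |
| Refusal after starting | Yes | CFU |
| Adverse events | Yes | CFU |
| Deterioration on treatment | Yes | CFU |
| Complicating disease | Yes | CFU |
| Other | Yes | CFU |
| Alternative therapy | Yes | End |
| Death | No | End |
| Deterioration before treatment | Not started | End |
| Refusal before treatment | Not started | End |

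Death and both pre-treatment exits have their own rows. Alternative therapy is therefore the only reason that ends follow-up for a living patient who has begun treatment.

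**Step 2. What is still recorded.** Section 8.5.2.3.1 requires every death within 56 days of registration to be reported, so a leaver who dies by Day 28 has a known outcome and counts as a failure. Section 8.4.1 requires SAE reports up to 30 days after the last dose, and Section 8.5.2.2 requires Grade 3 and 4 AEs. These capture some deterioration, but not the ordinal score at Day 28. The gap is Day 28 status in survivors.

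**Step 3. The plan's own figure.** Section 13.6 assumes 80% against 92%, 132 per arm, a two-sided 0.05 level and an unpooled Z-test.

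- Required n per arm = (0.80×0.20 + 0.92×0.08)(1.960 + 0.842)² / 0.12² = 127.3. The pooled form gives 131.
- SE at 132 per arm = √[(0.1600 + 0.0736)/132] = 0.04207.
- Power = Φ(0.12/0.04207 − 1.96) = 81.4%, or 81.1% at the final boundary of 1.97 in Section 13.4.

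The stated 80% power is reproduced. Section 13.6 states no allowance for missing outcomes. The reference below is 12.0 points and 81.1%.

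**Step 4. Illustration.** The documents give no rate for alternative therapy, so all of these inputs are assumed:

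- share leaving, l: 5% placebo and 2% camostat (about 7 and 3 of 132);
- true Day 28 successes among leavers, s: 40%;
- leavers dead by Day 28, d: 20% or 40%, kept as failures. The remaining leavers (40% or 20%) are alive in respiratory failure.

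Surviving leavers are excluded, so the observed rate in an arm is (p − l·s) / (1 − l(1 − d)), on 132(1 − l(1 − d)) patients.

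*True 80% vs 92%*

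- d = 20%: placebo 0.780/0.960 = 81.25%; camostat 0.912/0.984 = 92.68%; difference 11.43 points. With n = 126.7 and 129.9, SE is 0.04152 and power is Φ(0.1143/0.04152 − 1.97) = 78.3%.
- d = 40%: placebo 0.780/0.970 = 80.41%; camostat 0.912/0.988 = 92.31%; difference 11.90 points. With n = 128.0 and 130.4, SE is 0.04213 and power is 80.3%.

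*No true effect, 80% in both arms*

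- d = 20%: 81.25% vs 0.792/0.984 = 80.49%; bias −0.76 points.
- d = 40%: 80.41% vs 0.792/0.988 = 80.16%; bias −0.25 points.
- Swapping the leaving rates between arms reverses both signs.

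**Step 5. Direction.** An arm's rate is unchanged only if success among its excluded survivors, s/(1 − d), equals the arm's true rate. Here that share is 50% or 67%, below both 80% and 92%, so both arms are inflated and the net effect depends on which is inflated more. With 5% leaving in each arm and a true 80% vs 92%, camostat becomes 0.900/0.960 = 93.75% or 0.900/0.970 = 92.78%. The difference is then 12.5 or 12.4 points, an overstatement.

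**The case against.** The strongest reply is that the row may hardly ever be used. Treatment lasts 14 days, and Section 7.1 lets physicians give any medicine they judge necessary, so starting another drug does not in itself take a patient off protocol treatment. Deterioration, the most outcome-related reason to switch, goes to CFU. The term is not defined. All of this stands: it limits the likely size, and no rate can be derived from the documents.

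Second, the Missing Data section only encourages continued visits, so it can be read as a retention aim. That is fair as to tone, but a site cannot encourage visits that the table has ended, and Section 10.4 names withdrawal as its only exception.

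Third, other data routes exist. The SAE window stays open past Day 28 for any patient dosed, and a discharged patient with no further hospital data is assumed not readmitted. These narrow the gap without closing it. Event reports do not give the Day 28 score, and the exclusion rule in Section 13.4 is the more specific one for the primary outcome.

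A reader might also bring in the differing denominators. Section 13.1 says "All patients meeting eligibility criteria who received at least 1 dose of study drug will be included in the analysis", while Section 13.3.1 uses "divided by the number of total patients enrolled for each treatment arm". That conflict arises for any missing outcome, whatever Section 10.3 says. It is a separate matter and adds no weight here.

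**Conclusion.** The contradiction is plain on the text: one row of Section 10.3 ends outcome follow-up for living, treated patients, against the Missing Data section and Section 10.4. Through the exclusion rule in Section 13.4 it can remove treated survivors from the primary analysis. It should be fixed. Confidence is high for the contradiction and does not extend to the size or direction of any effect.

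Under the assumed rates the effect is modest: 11.4 to 11.9 points in place of 12.0, power of 78% to 80% in place of 81%, and 0.25 to 0.76 points of bias when there is no true effect. With fewer leavers it would be negligible.

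Two stronger readings are tempting. The first is that every leaver is lost, deaths included. With the same leaving rates that gives 0.780/0.950 = 82.11% vs 0.912/0.980 = 93.06%, a difference of 10.96 points, with power of 76.1% and a null bias of 1.29 points. The documents do not support it, because deaths must be reported to Day 56 and would count as failures. The second is that the trial is biased in a known direction, for example against camostat. The documents give neither the leaving rates by arm nor the outcomes of leavers, and equal leaving can overstate the effect. Nor does the row make the sample size of 264 wrong.

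**What to change.** In the Section 10.3 table, change the alternative-therapy entry from no follow-up to CFU. State that vital status and ordinal score are collected at Day 28 and Day 56 by visit, phone or chart unless the patient withdraws consent to follow-up. Leave the death row and the two pre-treatment rows as they are. No change to Section 13.4 is needed for this point, since it already analyses dosed patients as randomised.

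The cost is one table cell and a phone or chart check at two time points for a few patients. Footnotes l and o to the test schedule already provide for remote assessment of discharged patients. Sample size, test and treatment are unchanged. The change concerns outcome collection only and implies nothing about which therapy a patient should receive or when treatment should stop.
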